4.2.2 Per-protocol (PP)

Per-protocol (PP) analyses will be conducted in participants who do not have any intercurrent events (ICEs). ICEs include:

- ICE1: Non-respect of the treatment strategy, including cross-over (use phytotherapy in the control group or not used Kaloba® in the intervention group), non-adherence to treatment (adherence is defined as missing the treatment at least 50% over the period of symptoms (and maximum for 7 days), use of antibiotics at baseline, use medications other than those authorized (exclusion criteria 12, section 5.2), discontinuation of treatment in the intervention group (e.g., due to AEs or lack of efficacy), already using Kaloba® or Umckaloabo® in the control group (exclusion criteria 11, section 5.2).
- ICE2: Inclusion despite presence of an exclusion criterion (criteria 1 to 10, section 5.2) or lack of an inclusion criterion (criteria 1 to 3, section 5.2).
- ICE3: Terminal events, such as death.

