4.3 Estimands

We define the following estimands for the outcomes.

Estimand E1.1: This estimand quantifies the effectiveness of the treatment assessed with the reduction of symptom severity (co-primary outcome).

Outcome of interest: Number of days needed to achieve a 50% reduction on the Acute Bronchitis Severity Score (ABSS) after peak of symptoms, assessed at max. 22 days. The peak of symptoms is defined by the highest ABSS (or the initial score if there is no peak). This is a normally distributed count outcome (3).

Population-level summary measure of outcome: adjusted* mean difference.

Participant-set of interest: FAS.

Handling of intercurrent events: All participants are included.

Handling of missing data: Missing data will be multiple imputed (see section 6.4).

* 1) Adjusted for the type of recruitment (PCP/walk-in clinic) and 2) adjusted for the following factors at baseline: type of recruitment, age, sex, level of education, smoking status, beginning of symptoms (number of days), baseline ABSS, and prescriptions for corticosteroid containing oral medication or inhalers (yes/no), including Prednisone, Symbicort, and Vannair.

Estimand E1.2: This estimand quantifies the effectiveness of the treatment assessed with the reduction of symptom severity (co-primary outcome) in the PP population.

Outcome of interest: Same as estimand 1.1.

Population-level summary measure of outcome: same as estimand 1.1.

Participant-set of interest: PP.

Handling of intercurrent events: Participants with ICE1-3 are excluded from the analysis. The data will be weighted according to inverse probability weighting for ICE 1 and 2 (see section 6.2.2).

Handling of missing data: As ICE cannot be assessed in participants who drop out or are lost to follow-up, we will not use multiple imputation. We will use inverse probability of attrition weights to account for attrition and multiple imputation for missing baseline covariates (see section 6.4).

SAP for PHYTOBRONCH	Version of SAP: 1	
Based on template: CTU_STA_TEM-11; v5.0.0	Valid from: 20.03.2025	Page 8 of 15

Estimand E2.1: This estimand quantifies the efficacy of the treatment assessed with the proportion of antibiotics use (co-primary outcome).

Outcome of interest: Use of antibiotics after the initial visit (binary).

Population-level summary measure of outcome: adjusted* risk ratio.

Participant-set of interest: FAS.

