Handling of intercurrent events: All participants are included. Participants who took antibiotics at baseline will be considered as failures (having antibiotics).

Handling of missing data: Missing data will be multiple imputed (see section 6.4).

* Same adjustment as E1.1. If there are too few participants, we will use analyses adjusting separately for each covariate + type of recruitment.

Estimand E2.2: This estimand quantifies the efficacy of the treatment assessed with the proportion of antibiotics use (co-primary outcome) in the PP population.

Outcome of interest: same as estimand 2.1.

Population-level summary measure of outcome: same as estimand 2.1.

Participant-set of interest: PP.

Handling of intercurrent events: Participants with ICE1-3 are excluded from the analysis. The data will be weighted according to inverse probability weighting for ICE 1 and 2 (see section 6.2.2).

Handling of missing data: As ICE cannot be assessed in participants who drop out or are lost to follow-up, we will not use multiple imputation. We will use inverse probability of attrition weights to account for attrition and multiple imputation for missing baseline covariates (see section 6.4).

Estimand E3.1: This estimand quantifies the incidence of AEs and SAEs.

Outcome of interest: Presence of any adverse or severe adverse event (binary) during the follow-up (up to 22 days).

Population-level summary measure of outcome: adjusted^{*} hazard ratio.

Participant-set of interest: SAF.

Handling of intercurrent events: All participants are included.

Handling of missing data: No missing data, participants are censored when the study ends (at day 22) or at the day of last contact.

* 1) Adjusted for the type of recruitment (PCP/walk-in clinic) and 2) adjusted for the following factors at baseline: type of recruitment, age, sex, level of education, smoking status, beginning of symptoms (number of days), and baseline ABSS. If there are too few participants, we will use analyses adjusting separately for each covariate + type of recruitment.

Estimand E3.2: This estimand quantifies the incidence of AEs and SAEs.

Outcome of interest: same as estimand 3.1.

Population-level summary measure of outcome: same as estimand 3.1.

Participant-set of interest: SAF without ICE2.

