5.2 Eligibility

The target study participants are outpatients with acute bronchitis (with or without COVID-19).

Inclusion criteria are:

- 1. At least 18 years old
- 2. Consulting for the first time as part of this bronchial episode
- 3. Consulting for:
 - a. Acute cough (≤ 8 days) as the main symptom
 - b. Illness (≤ 8 days) in which cough is not the main symptom, but the PCP believes that acute bronchitis is the most likely diagnosis

Exclusion criteria are:

- 1. Infection requiring antibiotics
- 2. Pneumonia
- 3. Non-infectious causes (COPD, asthma, pulmonary embolism, heart failure, gastro-esophageal reflux, allergy)
- 4. Incapacity of judgment (dementia, psychosis or severe depression)
- 5. Important risk of bleeding (severe thrombocytopenia and anticoagulant intake)
- 6. Inability to complete the diary
- 7. Pregnancy or breastfeeding
- 8. Immunological deficiencies
- 9. Severe hepatic disease
- 10. Known hypersensitivity to Pelargonium sidoides extract or excipients of the trial medication
- 11. Currently taking Kaloba® or Umckaloabo® for this current episode of acute bronchitis
- 12. Taking anticoagulants, immunosuppressants, chemotherapy or immunotherapy

A CONSORT patient flow diagram will be drawn.

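### Exclusion criterion 11 (prior Kaloba use) is an intercurrent event in the control arm only, so the per-protocol estimands and safety estimand E3.2 treat identical eligibility breaches differently by arm

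*Combined protocol and SAP*

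**What the plan says.** Section 5.2 lists exclusion criterion 11 as "Currently taking Kaloba® or Umckaloabo® for this current episode of acute bronchitis". It applies at enrolment and does not refer to the arm.

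Section 4.2.2 sorts eligibility breaches into two kinds of ICE. ICE2 is "Inclusion despite presence of an exclusion criterion (criteria 1 to 10, section 5.2"), so it does not reach criteria 11 and 12. Those two appear under ICE1, the category for departures from the treatment strategy. Criterion 12 enters without an arm limit: "use medications other than those authorized (exclusion criteria 12, section 5.2"). Criterion 11 enters with one: "already using Kaloba® or Umckaloabo® in the control group (exclusion criteria 11, section 5.2").

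The consequences follow from three rules:

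- **PP set (section 4.2.2):** "Per-protocol (PP) analyses will be conducted in participants who do not have any intercurrent events (ICEs").
- **E1.2 and E2.2 (section 4.3):** "Participants with ICE1-3 are excluded from the analysis".
- **E3.2 (section 4.3):** "Participant-set of interest: SAF without ICE2", with ICE1 handled by censoring at the deviation.

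Section 6.2.1 names the PP set next to the full analysis set in the primary analysis, so the PP results are not peripheral.

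**The concern.** Being on Kaloba at enrolment is fixed before randomisation, so such participants are expected in equal proportion in both arms. Removing them from both arms, or from neither, keeps the arms comparable on this characteristic. Removing them from control alone does not: the Kaloba arm of the PP set then contains a type of participant that the control arm cannot contain. Any difference between prior users and others in symptom course, antibiotic use or adverse events then enters the estimated treatment effect.

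Criterion 11 is the only eligibility criterion whose breach is handled differently by arm. The PP set, meant to be free of ineligible inclusions, keeps some of them in one arm by definition.

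**Working it through.** **Step 1. The plan's own figure.** Section 2.3 gives 420 participants (210 per group), from 60% versus 45% antibiotic use at two-sided alpha 0.025 and 80% power. With z = 2.2414 and 0.8416 and a mean proportion of 0.525:

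n = [2.2414 × √(2 × 0.525 × 0.475) + 0.8416 × √(0.60 × 0.40 + 0.45 × 0.55)]² / 0.15² = 209.4, so 210 per arm and 420 in total.

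The symptom calculation (difference 1 day, SD 3 days) gives 173 per arm, 346 in total, with the t-based formula. Both figures reproduce. The point does not depend on them; 210 per arm is used below only for scale.

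**Step 2. One criterion-11 breach with no other ICE, followed through each rule.**

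| | Randomised to Kaloba | Randomised to control |
|---|---|---|
| ICE1 | No (clause limited to control) | Yes |
| ICE2 | No (stops at criterion 10) | No (stops at criterion 10) |
| PP set, E1.2 and E2.2 | Kept | Excluded |
| E3.2 | Followed to day 22 | In the set, but censored at the deviation |

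For E3.2 the SAP gives no rule for dating this deviation. If it is dated to when use began, which is before randomisation, the control participant contributes essentially no person-time.

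**Step 3. Can weighting or adjustment repair it?** The ICE1 weights (section 6.2.2) use site type, age, sex, education, symptom duration and baseline ABSS. Prior Kaloba use is not among them, nor among the outcome-model covariates in section 4.3. Adding it would not help: every control prior user has ICE1 by definition, so none is left in the control PP set to be weighted up. E3.2 is weighted for ICE2 only.

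**Step 4. Size.** The documents give no frequency of prior use and no outcome difference for prior users, so both are assumptions. Let f be the share of prior users in each arm.

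- *Symptom outcome (E1.2).* Let d be the prior users' outcome minus that of other participants, in days. The Kaloba PP mean is (1 − f)μ + f(μ + d) = μ + fd. With no true effect the control PP mean is μ. The shift is f × d.
- *Antibiotic use (E2.2).* With no true effect, a 60% base risk and prior users 15 points lower, RR = [0.60(1 − f) + 0.45f] / 0.60 = 1 − 0.25f. With prior users 15 points higher, RR = 1 + 0.25f.
- *Adverse events (E3.2).* With no true effect and a prior-user hazard r times that of others, HR ≈ 1 + f(r − 1). Controls are taken as censored at baseline.

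| f (assumed) | Participants per 210 | E1.2 shift, d = ±1 day | E1.2 shift, d = ±2 days | E2.2 RR, 15 points lower / higher | E3.2 HR, r = 0.5 / 1.5 |
|---|---|---|---|---|---|
| 1% | 2.1 | ±0.01 | ±0.02 | 0.9975 / 1.0025 | 0.995 / 1.005 |
| 2% | 4.2 | ±0.02 | ±0.04 | 0.995 / 1.005 | 0.99 / 1.01 |
| 5% | 10.5 | ±0.05 | ±0.10 | 0.9875 / 1.0125 | 0.975 / 1.025 |
| 10% | 21 | ±0.10 | ±0.20 | 0.975 / 1.025 | 0.95 / 1.05 |

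For scale, the design difference is 1 day. The standard error of a mean difference with 210 per arm and SD 3 is 3 × √(2/210) = 0.29 days, and larger in a smaller PP set. A shift of 0.10 days is about a third of that. Under a symmetric rule the shift is 0 and both ratios are 1.

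**The case against.** The strongest defence is that the arm limit is deliberate. ICE1 concerns departures from the assigned strategy: a control on Kaloba is contaminated, whereas a Kaloba-arm participant on Kaloba is taking what was assigned. That plausibly explains the wording, although the SAP does not say so. It does not justify the result. Criterion 11 is an eligibility criterion, ICE2 exists for ineligible inclusions, and prior use precedes randomisation.

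It can also be said that the ICE1 list is introduced as examples and might be read to cover the Kaloba arm. An express limit to controls points the other way, and no other section catches these participants. Section 5.4 will show protocol violations by group, so the breaches should be visible, but a count does not correct the estimate.

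The objections on size and direction do stand. These are breaches of an explicit exclusion and are probably few.

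A reader might also infer more than the documents support:

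- *That prior users are already tolerant, so the asymmetry flatters Kaloba's safety.* Criterion 11 speaks only of current use. Tolerance is plausible but is not stated.
- *That efficacy is biased in Kaloba's favour.* Prior users who still consult may be early responders or people for whom the product has not worked. E1.2 also counts days from the peak score during the study (section 6.1), so treatment days before enrolment do not enter the count directly.
- *That E3.2 drops control prior users from its set.* It censors them. This amounts to removal only if the deviation is dated at or before baseline.
- *That the fault lies in a covariate missing from the weights.* Step 3 shows that adding it would change nothing.

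**Conclusion.** The asymmetry is explicit in the text, and nothing elsewhere in the plan removes it. It affects E1.2, E2.2 and E3.2. It leaves E1.1, E2.1 and E3.1 untouched, since those apply no ICE-based exclusion or censoring.

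The direction of bias cannot be determined from the documents, and the size is probably small. Over an assumed 1% to 10% prior users, the PP mean difference shifts by about 0.01 to 0.10 days for each day by which prior users differ, and the E3.2 hazard ratio by about 0.5% to 5% if their adverse-event hazard is half that of others. These figures assume equal prior use in both arms and, for the ratios, no true treatment effect; the E3.2 figure also assumes censoring at baseline. The case for a change rests on an avoidable post-randomisation selection with a cheap remedy, not on a large expected bias.

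**What to change.** Treat criterion 11 in the same way in both arms. In section 4.2.2, extend ICE2 to exclusion criteria 1 to 11 and delete the control-only clause on criterion 11 from ICE1. Keep phytotherapy use by controls after randomisation under ICE1 as cross-over. E1.2, E2.2 and E3.2 then exclude prior users from both arms, and the E3.2 dating question falls away because ICE2 participants leave the set outright.

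The costs are small. A few more Kaloba-arm participants leave the PP and E3.2 sets. These breaches are then weighted by the ICE2 model, which uses site type only, instead of the six-covariate ICE1 model. The planned sample size of 420 is unchanged.

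An alternative with less rewording is to keep criterion 11 in ICE1, remove the control-group limit, and state that the event is dated at baseline for E3.2. This retains the richer ICE1 weights for E1.2 and E2.2.

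Either way, report criterion-11 breaches by arm within the section 5.4 summary. As the trial is open-label, settle the rule before database lock.

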4.2.3 Safety population (SAF)

The safety population (SAF) will be participants who received at least one medication (Kaloba® or usual care).

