2.1 Trial design

This is a pragmatic, open-label, superiority randomized controlled trial, which takes place in ~40 PCP in practices and 5 walk-in clinics. The intervention group receives Kaloba® for 7 days and up to 21 days. The control group receives usual care, with symptomatic treatments freely chosen by the PCP (phytotherapy excluded). Usual care is not standardized between PCPs. A delayed use of antibiotics can be used in both groups. Prescription of paracetamol is allowed, as well as any routine medication pre-reviewed by the PCP and not counter-indicated.

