AEs and SAEs. The first secondary endpoint will include AEs, predefined according to the dictionary MedDRA and SAEs, defined according to the HRA. Assessments of severity (5 categories, from grade 0 to 5) and causality (5 categories, from "not related" to "definitely related") will also be evaluated. We will compute a single endpoint with 0=no AE or SAE during the study and 1=at least one AE or SAE during the study period. We will also create separate endpoints for AEs and SAEs and types of AEs/AEs. The date of the (S)AEs will also be recorded, to capture the time until (S)AE.

SAP for PHYTOBRONCH	Version of SAP: 1	
Based on template: CTU_STA_TEM-11; v5.0.0	Valid from: 20.03.2025	Page 12 of 15

PCP agreement to participate in the study. The second secondary endpoint will assess whether the PCP agrees to participate in the study. Participation will be defined as signing the agreement and enrolling participants. Non-participation will be defined as refusing or signing but not enrolling participants.

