6.2.2 Secondary analyses

The secondary analysis will be done according to the FAS (ITT) and PP sets specified in section 4.2. Models will also be adjusted for the stratification factor and relevant covariates, with bootstrapped standard errors, as described for the primary analysis. Effects will be shown using marginal point estimates (accounting for adjustment variables) and 95% confidence intervals.

For the first secondary endpoint, AEs and SAEs, we will use a Cox regression, e.g.:

stset timevar, failure(y) id(idvar)

bootstrap, reps(1000) seed(XXX): stcox x1 x2

We will use multiple imputation to handle missing values on covariates (see section 6.4). There won't be missing values on (S)AEs, as participants who drop out from the study will be right-censored. If there is collinearity between covariates, we will remove one colinear variable based on theoretical reasons. If the assumption of proportionality of hazard is not met, we will stratify on the problematic variable(s).

For the second secondary endpoint, *proportion of PCP who agree to participate*, we will calculate a percentage with a 95% confidence interval, using Wilson intervals which are superior for small samples without being overly conservative like exact methods (6), e.g.:

cci proportions n x, Wilson

For analyses on the PP set, we will run the same analyses as described in section 6.2.1. In addition, we will use inverse probability weighting for ICE1 and ICE2. We will derive stabilized weights separately and combined them by multiplying them. The covariates used to create weights are the following. For ICE1, we will use for GP/walk-in clinic, age, sex, education, beginning of symptoms (number of days), and baseline ABSS. For ICE2, we will use for GP/walk-in clinic. We will runcate weights at

SAP for PHYTOBRONCH	Version of SAP: 1	
Based on template: CTU_STA_TEM-11; v5.0.0	Valid from: 20.03.2025	Page 13 of 15

the 99th percentile. The weights will then be used in the main adjusted model to re-balance randomization groups. We will check whether balance was achieved using standardized mean/proportion differences, which should be lower than .25 (7, 8). As balance may not be achieved using multiple imputation, we will use simple imputation in models using inverse probability weighting.

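### The safety set requires receipt of a medication, so controls managed without a drug may be left out of the adverse-event comparison, with bias of unknown size and direction

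*Combined protocol and SAP*

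**What the plan says.** Section 4.2.3 defines the safety set (SAF): "The safety population (SAF) will be participants who received at least one medication (Kaloba® or usual care"). In section 4.3, estimand E3.1 names it as the analysis set ("Participant-set of interest: SAF"). E3.2 uses the same set without participants who have the eligibility-related intercurrent event, ICE2.

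Section 2.1 describes the comparator: "The control group receives usual care, with symptomatic treatments freely chosen by the PCP (phytotherapy excluded"). It adds: "Usual care is not standardized between PCPs", and, on other drugs, "Prescription of paracetamol is allowed, as well as any routine medication pre-reviewed by the PCP and not counter-indicated". Section 2.8 says that the trial is not blinded.

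The E3.1 outcome is "Presence of any adverse or severe adverse event (binary) during the follow-up (up to 22 days"). Section 6.1 codes it without reference to cause: "We will compute a single endpoint with 0=no AE or SAE during the study and 1=at least one AE or SAE during the study period".

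For the same endpoint, section 6.2.2 opens with different sets: "The secondary analysis will be done according to the FAS (ITT) and PP sets specified in section 4.2". The SAF is not named there.

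The SAP does not say whether a control managed without a drug has received usual care for this purpose, whether paracetamol or routine medication counts as a qualifying medication, or whether SAF participants are grouped as randomised or as treated.

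**The concern.** In the Kaloba arm the assigned treatment is itself a medication, so anyone who starts it enters the SAF. In the control arm, entry depends on whether the physician chooses to give a drug and the patient takes it, both after allocation is known. The entry rule therefore works differently in the two arms and rests on a post-randomisation event.

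If drug-free controls differ from medicated controls in their risk of an adverse event, E3.1 no longer compares Kaloba with usual care as delivered. It compares Kaloba with the medicated part of usual care. Should the omitted controls have fewer events, the control rate rises and Kaloba looks safer than it is, which is the more troubling direction for a safety comparison. Separately, a definition open to two readings leaves the choice of set to be made once open-label data are in hand.

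**Working it through.** **Inputs from the documents.** 1:1 allocation (section 2.2); 420 participants, 210 per group (section 2.3); SAF rule (4.2.3); E3.1 set and outcome (4.3); free choice of control treatment (2.1). The SAP gives no adverse-event rate and no expected share of drug-free controls.

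**The plan's own figure.** The sample size matters here only because it fixes the arm size. For 60% against 45%, two-sided alpha 2.5%, power 80%, pooled variance and no continuity correction:

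n per arm = [2.2414·√(2·0.525·0.475) + 0.8416·√(0.60·0.40 + 0.45·0.55)]² / 0.15² = 209.4, rounded up to 210, or 420 in total. This matches the SAP.

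**Distortion factor.** Let f be the share of controls given no drug and k their adverse-event risk relative to medicated controls. Let p_C be the risk over all controls and p_M the risk in medicated controls.

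- p_C = (1 − f)·p_M + f·k·p_M, so p_M = p_C / (1 − f + f·k).
- If no Kaloba participant is excluded, SAF risk ratio = all-randomised risk ratio × (1 − f + f·k).
- If a share g of the Kaloba arm also takes no medication, with relative risk m, the factor becomes (1 − f + f·k) / (1 − g + g·m). Exclusions in that arm can offset or add to the effect.

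**Results for a true risk ratio of 1.00 and g = 0. All f and k are assumed.**

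| f | Controls left of 210 | k = 0 | k = 0.5 | k = 1 | k = 1.5 | k = 2 |
|---|---|---|---|---|---|---|
| 5% | 200 | 0.95 | 0.975 | 1.00 | 1.025 | 1.05 |
| 10% | 189 | 0.90 | 0.95 | 1.00 | 1.05 | 1.10 |
| 20% | 168 | 0.80 | 0.90 | 1.00 | 1.10 | 1.20 |
| 30% | 147 | 0.70 | 0.85 | 1.00 | 1.15 | 1.30 |

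**On the hazard-ratio scale.** With an assumed 20% risk in both arms and no censoring, HR ≈ ln(1 − 0.20) / ln(1 − p_M). At f = 20%:

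- k = 0.5: p_M = 0.20/0.90 = 22.2%, HR about 0.89
- k = 1: p_M = 20.0%, HR 1.00
- k = 1.5: p_M = 0.20/1.10 = 18.2%, HR about 1.11

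**A scenario with k below 1.** Assume 15% risk in medicated controls and 5% or 8% in drug-free controls, so k = 0.05/0.15 = 0.33 or 0.08/0.15 = 0.53. The factor is:

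- f = 5%: 0.967 to 0.977, so the ratio is 2–3% too low
- f = 10%: 0.933 to 0.953, so 5–7% too low
- f = 20%: 0.867 to 0.907, so 9–13% too low

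**Against sampling error.** With 210 per arm and 15% risk in each, the standard error of the log risk ratio is √(2·0.85/(210·0.15)) = 0.23. A 95% interval around 1 runs from about 0.63 to 1.58. A shift of 2–7% is small beside that; one of 9–13% is less so, though still well inside it.

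**The case against.** A reader might infer that drug-free controls are certain to be excluded and that the result must flatter Kaloba. The documents support neither.

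- **Exclusion.** The bracket in section 4.2.3 lists usual care as qualifying, so a control managed without a drug could be read as having received it. The SAP never mentions drug-free controls, and lack of standardisation shows variation, not absence of drugs. This stands as a reason to call the wording ambiguous. It does not clear it: the governing requirement is receipt of a medication, and either reading leaves something to be written down.
- **Direction.** Patients given no drug are spared its side effects, and physicians may withhold drugs from milder cases, so k below 1 is plausible. But the endpoint counts any event regardless of cause, and nothing in the SAP rules out k of 1 or more. This objection stands in full.
- **Size.** Every f, k and event rate above is assumed. A range that fixes k near 0.33–0.53 cannot show nil or reversed bias; the wider table can.
- **Section 6.2.2.** It names the full analysis set, which is all randomised participants by assigned group, so an analysis keeping every control may already be intended. That helps only if it is the rule that governs. It contradicts E3.1 and E3.2, and E3.1's own statement that all participants are included, given under intercurrent events, sits uneasily with a restricted set.

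**Conclusion.** The point holds as a defect of definition. Taken literally, the SAF selects controls on an open-label, post-randomisation decision with little counterpart in the Kaloba arm; at best, the status of drug-free controls is undefined. The conflict between section 6.2.2 and E3.1/E3.2 over the analysis set can be seen in the text alone and needs no assumption.

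The distortion of the risk ratio is 1 − f + f·k, assuming no exclusions from the Kaloba arm. With assumed f of 5–20% and k of 0.33–0.53 the ratio is about 2–13% too low; at k = 1 it is undistorted, and at k above 1 Kaloba looks less safe than it is. The documents fix neither f nor k, so a definite bias in Kaloba's favour cannot be claimed. The change is still worth making before the data are analysed, because it costs little and removes the selection of controls whatever its direction.

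**What to change.** - Redefine the SAF so that every participant randomised to usual care is included, whether or not any drug was prescribed or taken.
- State the entry rule for the Kaloba arm, whether paracetamol or routine medication counts, and whether participants are grouped as randomised or as treated. Cover Kaloba-arm participants who took none and controls who took it; section 4.2.2 foresees the first and, under use of phytotherapy by controls, the second.
- Report adverse and serious adverse events in all randomised participants by assigned group, as the main or a sensitivity analysis. Keep any exposure-based grouping supplementary: placing everyone who took no Kaloba under usual care would move Kaloba-arm non-takers into the comparator and bring back selection after randomisation.
- Reconcile section 6.2.2 (FAS and PP) with E3.1 and E3.2 (SAF), so that one set is named for each safety analysis.

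The cost is SAP wording and at most one extra model run. The diaries and telephone calls in section 2.7 apply to participants in general, so no new data collection appears necessary. The downside is that a few controls with no drug exposure enter the safety set, but they are part of usual care as delivered.
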